## Randomized, Double-Blind, Placebo-Controlled Part:

- It is recommended to perform a liver biopsy in a subject that discontinues treatment between week 24 to week 72 unless there is an available biopsy within the past 6 months.
- It is recommended to perform a liver biopsy in a subject that discontinues treatment between 2-years to 5-years, unless there is an available biopsy within the past 6 months.

## 8.4 Investigational Medicinal Products/Study Drugs

#### 8.4.1 Treatment Administration

Open-Label Part: Aramchol 300mg will be taken twice daily (BID).

Randomized, Double-Blind, Placebo-Controlled Part: Aramchol 300mg or matching placebo will be taken twice daily (BID).

Two tablets should be taken by mouth daily, one after breakfast in the morning and the other after a meal in the evening.

## 8.4.2 Method of Assigning Subjects to Treatment Groups

## **Open-Label Part:**

Subjects, including those already randomized to Aramchol 300mg BID or Placebo, will be randomized in a ratio of 1:1:1 to receive Aramchol 300mg BID according to the below grouping:

- Group A: The post-baseline liver biopsy will be conducted at week 24
- Group B: The post-baseline liver biopsy will be conducted at week 48
- Group C: The post-baseline liver biopsy will be conducted at week 72

Randomization in the Open-Label Part will employ a semi-minimization algorithm to balance the 3 groups in number of subjects, distribution of subjects according to fibrosis score (F1, F2 and F3), presence or absence of T2DM, and prior exposure to Aramchol 300mg BID. F1 subjects will be capped to enroll no more than 30 subjects.

Subjects already randomized and in the Randomized, Double-Blind, Placebo-Controlled Part in the selected sites participating in the Open-Label part will be given the option to switch to the Open-Label Part.

Randomization in the Open-label Part will employ a semi-minimization algorithm to balance the 3 groups in number of subjects, distribution of subjects according to fibrosis score (F1, F2 and F3), presence or absence of T2DM, and prior exposure to Aramchol 300mg BID. F1 subjects will be capped to enroll no more than 30 subjects.

## Randomized, Double-Blind, Placebo-Controlled Part:

An eligible subject will randomly be allocated to treatment with Aramchol or matching placebo based on a randomization scheme employing a 2:1 assignment ratio, respectively, using permuted blocks stratified by country/geographical region (CGR) and by baseline Fibrosis stage (F2 or F3).

	 	

## 8.4.3 Study Blinding and Blinding Plan

## **Open-Label Part:**

All subjects will receive Aramchol 300mg BID.

## Randomized, Double-Blind, Placebo-Controlled Part:

Aramchol 300mg BID or matching placebo will be administered in a blinded manner. To maintain the blind, Aramchol and matching placebo capsules will have identical appearance and will be packaged in identical bottles.

Participating subjects, Investigators, the Sponsor and any personnel involved in subjects' assessments, monitoring, analysis and Data Management will be kept blinded to the treatment assignment, excluding the designated personnel in clinical supply vendor and the RTSM vendor.

### **ARMOR Study**

All liver biopsies will be centrally evaluated while the assessor is blinded to treatment assignment as well as to other parameters including site and sequence or indication (screening biopsy or week 72 biopsy or biopsy due to suspicion to progression to cirrhosis).

Adjudication committee members will be blinded to treatment assignment.

The DMC will consist of independent physicians with expertise in liver disease and internal medicine and an independent biostatistician, all with prior experience and expertise in clinical trials. An Independent Unblinded Statistician will prepare the reports for review by the DMC.

Unblinded safety reports if required for regulatory submissions as well as reporting of Suspected Unexpected Serious Adverse Reactions (SUSARs) will be handled by dedicated personnel. For these purposes, unblinding will be performed on an individual subject's basis. The Sponsor will remain blinded to that individual subject's treatment assignment.

In case of emergency code breaking, when the study drug assignment is needed to make treatment decisions for the subject, the Investigator may unblind the subject's drug assignment. The unblinded subject will be withdrawn from the study. In such cases of emergency unblinding, subject's treatment assignment will not be revealed to the Sponsor.

Analysis of the Histology-Based primary endpoint will be conducted when 1000 subjects complete their initial treatment period of 72 weeks (or terminated earlier). For the purpose of the conduct of these analyses which may be followed by a marketing authorization application, the Sponsor will establish a special taskforce firewalled from the study team. The taskforce will be led by a Sponsor management team member not directly involved in the ongoing management of the study. To maintain the integrity of the final post-Week 72 analyses, only a minimal number of personnel belonging to this taskforce will be exposed to the subject -level data, primarily to facilitate regulatory filings and required public disclosures.

Furthermore, study subjects, Investigators, and the Sponsor personnel involved in the ongoing study management and any personnel involved in subjects' assessments, monitoring, and Data Management will remain blinded to treatment assignment.

Following the conduct of the Histology-Based milestone analyses, major findings may be publicly disseminated by the Sponsor in accordance with 21 CFR 312.7. To preserve study blinding, trial integrity, subject's adherence and retention, only grouped level summary of results of the Histology-Based analyses including key secondary as well as potentially exploratory endpoints planned to be analyzed at this study milestone will be disseminated. Summary safety findings will also be disseminated.

Study integrity and blinding will not be compromised by the public dissemination of information due to the following major reasons: 1) the individual subject treatment assignment and data listings will only be shared with the Sponsor's dedicated taskforce and with regulatory authorities. 2) The publicly disseminated information will be on a "by group" basis. 3) The observed proportions of Histology-Based outcomes will not allow determining individual subject assignment. 4) The observed proportions of adverse events will not allow determining individual subject assignment.

A more detailed Statistical Analysis Plan (SAP) covering the analyses of the Histology-Based data as well as the Clinically-Based data at EoS was submitted prior to study initiation. SAP amendment will also be prepared and submitted prior to revealing of the blind for the analysis of the Histology-Based data.

## 8.4.4 Emergency Code Breaking

Open-Label Part: Not applicable since all subjects will receive Aramchol 300mg BID.

## Randomized, Double-Blind, Placebo-Controlled Part:

In case of any emergency as per the Investigator criteria or pregnancy, when the study drug assignment is needed to make treatment decisions for the subject, the Investigator may unblind the subject's drug assignment. The unblinded subject will be withdrawn from the study. The subject should remain in the study for follow-up until resolution or stabilization of the event.

Unblinding is performed in the Interactive Web Response System (IWRS). The process includes the following steps:

- Confirming the identity of the subject
- · Confirming the unblinding request
- Entering the unblinding reason
- Entering a password

	_

## 8.5 COVID-19 Contingency measures

## 8.5.1 General

Due to the COVID-19 pandemic the study subject may be either not allowed or unwilling to attend a regularly scheduled study visit or the visit may otherwise not be able to take place at the study site per standard practice. In that case contingency measures described in Sections 8.5.2 through 8.5.8 may potentially be applied according to the following general guidance:

- Local regulations and ordinances pertaining to the COVID-19 pandemic must always be followed and the safety of study subjects and research team must be assured.
- Every effort must be made to complete the full scope of the study visit activities and procedures. Any deviation from the standard practice and procedures of in person visit at the study site and use of the allowed contingency measures, must be clearly documented and flagged as COVID-19 related, and reported to the EC/IRB as applicable.
- Study subjects must be informed of any change in the study conduct that may be implemented under these contingency measures and verbal agreement documented.
- The contingency measures DO NOT APPLY to Screening and Baseline visits.
- The contingency measures specified here do not contradict any local rules or regulations

#### 8.5.2 Alternative Location Visit

In case circumstances related to COVID-19 prevent holding the study visit at the standard site location the PI may identify an alternative location for holding the study visit (e.g. private clinic, outside of the hospital/study facility, subject home) so long as the alternative location provides an appropriate environment for a study visit (including privacy and appropriate physical conditions), the necessary equipment, including laboratory and study drug kits and personnel is available and the study subject agrees with the alternative location.

## 8.5.3 Interview by Phone or Video Conference

The PI may decide to hold the scheduled subject interview by phone or video conference instead of as a standard in person meeting in order to minimize the social interaction and time required for the actual physical visit. At the beginning of the interview the identification of the participants must be verified by both sides presenting themselves by full name, and the existence of proper privacy conditions for the subject must be confirmed and documented. The interview must be documented as a phone/video conference interview in the subject file.

## 8.5.4 Necessary data collection requirements

In order for a visit to qualify as a study visit and to allow a new drug kit to be dispensed as part of the visit, the following essential visit activities must be performed:

- (a) Subject interview including changes in health condition, adverse events, changes in medication, and confirmation of study drug intake as per instructions.
- (b) Safety laboratory measurements including all tests defined in the protocol for the specific visit, with the exception of blood draws for PK. In case the specific processing and storage requirements for PK testing cannot be assured, the visit can still qualify as a study visit even if blood for PK is not taken.

## 8.5.5 Study equipment and materials

Storing of study related equipment and material (i.e. documentation, study drug kits, lab specimens, lab kits, devices, etc.) outside the study site should be short term and limited to what is directly required for holding the study visit at the alternative location or subject home.

No equipment or material should be stored at the subject's home. In cases where equipment and materials are kept outside the study sites, it must be maintained securely and under the required storage conditions.

## 8.5.6 Study drug dispensing and used drugs bottles collection

In case study visit is performed at an alternative location, the following applies:

- Study drug dispensing must only take place in case the required data collection requirements (see Section 8.5.2) have been met.
- Allocation of study drug kit by the IRT system should be done per the standard normally
  followed at the study site. The allocated kit must be taken under appropriate storage
  conditions to the alternative location and dispensed to the subject during the study visit.
  A study drug kit may be delivered to the study subject by courier but must not be mailed.
- The allocated kit must be properly documented at the site as per standard practice and confirmation of delivery/receipt is documented in the subject file.
- Used study drug bottles should be collected if possible, but in case circumstances do not
  allow, the subject should be instructed to keep the old used bottles and return them at the
  earliest feasible time to the alternative location or study site. If returned to an alternative
  location or during in-home visits, the PI and study personnel or delegate are responsible
  for ensuring transport to the site and full count of returned study drug at the study site.

## 8.5.7 Laboratory Specimens

In case the study visit is conducted in an alternative location:

- Safety laboratory samples should be processed following standard procedure by the central laboratory if the central laboratory services are available.
- In case of disruption to the central laboratory operation or the courier service operation, processing of the laboratory samples by a local laboratory is allowed.
- Test results reported by the local laboratory should be reviewed by the PI and the results as well as the actual review of the results, should be documented in the subject file.
- Laboratory specimen collected during a visit conducted at an alternative location must follow the standard practices of maintenance, storage, shipment and documentation.

## 8.5.8 Additional contingency measures

In case of standard protocol-specified time windows cannot be met the following will apply:

- Screening time window will be extended to 12 weeks
- Allowable time window for the visits will be extended up\_to ± 14 days for visits during the first 3 months of treatment, and up to 21 days after the first 3 months of the study.

## 9 ASSESSMENTS & PROCEDURES

## 9.1 Liver Biopsy

#### 9.1.1 Open-Label Part

Includes the following liver biopsies:

[figure not shown]
- Baseline liver biopsy: Performed during screening (biopsies performed in the 9 months prior to randomization are acceptable and will be sent for central reading).
- A post-baseline scheduled liver biopsy: Performed based on randomization groups A, B, C at week 24 or 48 or 72 respectively. The biopsy should be performed from 2 weeks prior to the scheduled biopsy and up to 6 weeks after the scheduled biopsy
  - In order to more comprehensively explore the kinetics of histological outcome measures (e.g. are there subjects who may not show improvement in outcome at week 24, 48 or 72 but may improve with longer duration of treatment), a 2nd post-baseline liver biopsy sample will be collected for subjects whose post-baseline liver biopsy at week 24 or 48 or 72 does not show at least 1 stage improvement in fibrosis (fibrosis non-responders). The 2nd post-baseline liver biopsy sample will be collected 1 year later (i.e. at weeks 72 or 96 or 120 respectively

[figure not shown]
## 9.1.2 Randomized, Double-Blind, Placebo-Controlled Part

Includes the following scheduled liver biopsies:

- Baseline liver biopsy: Performed during screening (biopsies performed in the 6 months prior to randomization are acceptable and will be sent for central reading).
- **72 weeks liver biopsy:** Performed from 2 weeks prior to week 72 visit and up to 6 weeks after week 72

## 9.2 Fibroscan

Fibroscan will be performed at Screening, week 24 and every 24 weeks thereafter as at early termination/study completion.

- Screening Fibroscan: Fibroscan done in the 4 weeks prior to screening is acceptable
- Fibroscan is performed as part of the NITs assessment in the study
- Fibroscan is also used in the study as follow-up to assist in identifying subjects who
  might require definite diagnosis by biopsy.

Fibroscan recommendations are as follows:

#### 9.3 Abdominal Ultrasound

Abdominal ultrasound will be performed at Screening, week 24 and every 24 weeks thereafter as at early termination/study completion.

- Screening US: US done in the 3 months prior to screening is acceptable
- Abdominal US should include
  - RUQ abdominal US to assess for hepatocellular carcinoma (HCC), cholelithiasis, choledocholithiasis, cholecystitis, or presence of other hepatic abnormalities.
     Results will be recorded on a dedicated CRF page
  - Abdominal US is performed to assess for signs of HCC or signs of progression to cirrhosis (e.g. ascites, splenomegaly)

## 9.4 MELD score

MELD will be calculated at screening, baseline, weeks 12, and at every study visit thereafter and at early termination/study completion.

MELD Calculation will be done using the OPTN formula/calculator which requires the input of the following lab values – Bilirubin, Sodium, Creatinine and INR. (https://optn.transplant.hrsa.gov/resources/allocation-calculators/meld-calculator/)

[figure not shown]
#### 9.5 Pre-Defined Clinical Outcome Events

Pre-defined clinical events for the Clinically-Based endpoint will be adjudicated by an independent adjudication committee:

- All-cause mortality
- Liver transplant
- Histological progression to cirrhosis
- MELD score >15 if baseline MELD score was <12

- Hospitalization due to hepatic decompensation event(s)
  - Hepatic encephalopathy grade ≥2 (as assessed by West Haven scale)
  - Variceal bleeding

- New onset ascites requiring treatment
- Spontaneous bacterial peritonitis as assessed by either positive cell culture or cell count

#### 9.7 Pharmacokinetics

Blood sample for analysis of concentrations of Aramchol and its metabolites as well as for population PK will be collected at all study visits from week 4 until week 72 and every 24 weeks thereafter and at early termination/study completion. Subjects attending a site visit in the morning should take their dose as usual in the evening before the visit and should record the time of dosing. They should NOT take their dose on the morning of their visit until after the blood sample for PK has been drawn. Subjects attending a site visit in the afternoon should take their morning dose as usual and should record the time of dosing.

The Investigator will record the timing the subject has taken the last tablet prior to blood drawing and the time of PK sampling.

Samples will be used for pharmacokinetic endpoints analysis and safety if deemed necessary.

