#### Randomized, Double-Blind, Placebo-Controlled Part:

Screening: up to 8 weeks.

Treatment period: Subjects will remain on the same treatment assignment for up to 7 years.

**End-of-Study**: All 2000 subjects planned to be randomized into this study will receive Aramchol or matching placebo until EoS which will occur at the time when a total of 380 subjects will experience at least 1 pre-specified clinical event or at 5 years from last subject's randomization, whichever comes first.

Both study parts (Open Label Part and Randomized, Double Blind, Placebo Controlled Part):

**Study Visits:** All subjects will attend the following visits: Screening, Baseline, weeks 4, 8, 12, and every 12 weeks thereafter.

[figure not shown]
Visit scheduling for subjects who switch from the Randomized, Double-Blind, Placebo-Controlled Part to the Open-Label Part is dependent on prior exposure to Aramchol. Subjects that received active treatment will continue based on scheduled visits. Subjects that received placebo will start the scheduled visits from a Baseline visit

At the visit when the switch is performed, subjects will sign a new ICF and complete activities as applicable (e.g. laboratory, imaging, stool samples).

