# 8.2.5 Randomized, Double-Blind, Placebo-Controlled Part Scheduled visits (not including End of Study visit)

Following the Baseline visit, the following assessments will be performed during scheduled visits at Week 4, 8, 12, and every 12 weeks thereafter.

The following should be performed/assessed during the visit:

- Physical examination at weeks 24 and every 24 weeks thereafter
- Body measurements including weight and waist circumference at week 12 and every visit thereafter
- Vital signs including blood pressure, heart rate, respiratory rate, and temperature
- Dietary and lifestyle changes as well as change in physical activity regimen will be assessed, and subjects will be counseled
- Concomitant medications
- Adverse Events
- ECG
- Laboratory:

Fasting (8 hours) is required before the visit

- A urine pregnancy test in women of childbearing potential
- Complete blood count and serum biochemistry will be measured at every study visit
- o Renal function (creatinine and eGFR) will be measured at every study visit
- Coagulation at every visit
- CPK will be measured at weeks 24 and every 24 weeks thereafter
- Glycemic parameters: fasting glucose will be measured at every study visit. HbA1c,
   C-peptide, Insulin and HOMA-IR at weeks 12,24 and every 24 weeks thereafter
- Thyroid function (TSH, T3 and T4) will be measured at week 48
- MELD will be calculated at week 12, and at every visit thereafter
- Blood sample for PK will be collected from week 4 until 72 weeks and every 24 weeks thereafter
- Blood samples for potential biomarkers (including ProC3 and ELF), metabolomics and better understanding of mechanism of action will be collected at week 12 24, 48 and every 24 weeks thereafter
- Drug accountability
- Study drug dispensing
- Abdominal ultrasound (US) and Fibroscan will be performed at week 24 and every 24
  weeks thereafter
  - Abdominal US is performed to assess for signs of HCC or other RUQ new findings as well as signs of progression to cirrhosis (e.g. ascites, splenomegaly)

- Fibroscan is performed as part of the NITs assessment in the study. Scan should meet the minimal quality definition (subject fasting for a minimum of 3 hours and at least 10 valid shots with IQR≤30% of the value of the median)

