## 9.8 Biomarkers, Metabolomics Gene and Microbiome Analysis

- Blood samples for potential biomarkers (including but not limited to ProC3 and ELF), metabolomics and better understanding of mechanism of action will be collected at Screening, Baseline, weeks 12, 24, 48 and every 24 weeks thereafter and at early termination/study completion.
- Blood sample for gene analysis will be taken from subjects providing consent in a
  dedicated informed consent form (ICF) (subject to local regulations and approval),
  preferably at Baseline visit, but will be accepted at any other visit. Samples will be kept
  frozen for future analysis
- In the Open-Label Part, stool samples for analysis of microbiome and better understanding of mechanism of action will be collected at Baseline, weeks 4, 12, 24, 48 and 72 and at early termination (if prior to week 72).

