## 9.9.2 Safety Laboratory Evaluations

Subjects should fast for 8 hours prior to each visit that includes laboratory sampling.

The central laboratory will be responsible for providing preliminary and final laboratory reports to the sites and for sending "alert" values to both the Principal Investigator and Sponsor or a designee. The PI should review, comment, sign, and date the final laboratory reports. All out-of-range and "alert" laboratory values are to be evaluated by the PI for clinical significance and classified as:

- Abnormal, not clinically significant
- Abnormal clinically significant

Any clinically significant laboratory parameters observed at screening should be documented as medical history.

A new or worsening clinically significant laboratory value observed at any time after screening should be further assessed, monitored and documented as an AE on the AE eCRF.

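### For afternoon visits less than 8 hours after breakfast, the section 9.7 dosing instruction conflicts with the 8-hour pre-visit fast (minor)

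*Combined protocol and SAP*

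**What the plan says.** **Dosing.** Section 8.4.1 has two tablets a day, "one after breakfast in the morning and the other after a meal in the evening".

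**PK visits.** Section 9.7 collects PK samples at all visits from week 4 to week 72, every 24 weeks after that, and at early termination or completion. For morning visits it holds the dose: "They should NOT take their dose on the morning of their visit until after the blood sample for PK has been drawn". For afternoon visits: "Subjects attending a site visit in the afternoon should take their morning dose as usual and should record the time of dosing". The recorded items it names are timings: "The Investigator will record the timing the subject has taken the last tablet prior to blood drawing and the time of PK sampling".

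**Fasting.** Section 9.9.2 states: "Subjects should fast for 8 hours prior to each visit that includes laboratory sampling". Sections 8.2.3 to 8.2.6 and 8.2.8 repeat the 8-hour requirement for scheduled, end-of-study, 7-year and discontinuation visits. None distinguishes morning from afternoon.

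**What is drawn.** Under 8.2.5, "fasting glucose will be measured at every study visit", and so is serum biochemistry, which includes triglycerides (Table 6). Insulin, C-peptide and HOMA-IR are added at weeks 12, 24 and every 24 weeks. Section 8.2.3 has the same schedule for the open-label part. For biomarker and metabolomics samples, 9.8 says: "metabolomics and better understanding of mechanism of action will be collected at Screening, Baseline, weeks 12, 24, 48 and every 24 weeks thereafter".

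**Use.** The Synopsis lists week-72 changes in fasting glucose, fasting insulin, C-peptide, HOMA-IR and triglycerides as exploratory endpoints of the randomized part. Section 4.1.1 makes glycemic and lipid parameters secondary kinetics endpoints of the open-label part.

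**The concern.** For morning visits 9.7 reconciles dose and fast. For afternoon visits it does not, and the readable text does not say which rule gives way. A subject who arrives less than 8 hours after breakfast has two choices, and each loses something.

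- **Eat and take the tablet, as 9.7 and 8.4.1 together direct.** The fast is broken, so values labelled as fasting are not. Metabolomics samples from the same visit may be affected too.
- **Keep the fast and take the tablet without food.** The dose departs from 8.4.1. Section 3.2 reports 2.6-fold exposure after a high-fat, high-calorie meal compared with fasting, so the PK sample would carry variability that dose time and sample time do not explain. Section 4.3 plans to relate PK to patient factors and to response.

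The open-label part has no control arm, so fed values set against a fasted baseline could look like a change over time.

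**Working it through.** The plan gives no figure to reproduce. Clock times, shares, glucose rises and PK constants below are assumptions.

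**1. When the rules clash.** Earliest compliant visit = end of breakfast + 8 h.

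| Breakfast ends (assumed) | Earliest compliant visit |
|---|---|
| 06:00 | 14:00 |
| 06:30 | 14:30 |
| 08:00 | 16:00 |
| 09:00 | 17:00 |

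With breakfast ending at 06:30 or later, no visit from 12:00 to 14:00 complies. A visit 8 hours or more after breakfast has no conflict.

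**2. Visits where the clash can arise, up to week 72** (8.2.3, 8.2.5, 9.7, 9.8).
- PK, fasting glucose, triglycerides: weeks 4, 8, 12, 24, 36, 48, 60, 72 = 8 visits.
- Insulin, C-peptide, HOMA-IR: weeks 12, 24, 48, 72 = 4 visits.
- Metabolomics: weeks 12, 24, 48, 72 = 4 visits.

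Baseline is not exposed: 9.7 sampling starts at week 4, and 8.2.2 has the first dose taken on site after all visit activities.

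**3. Randomized part.** Let p be the share of week-72 values that are non-fasted and d the glucose rise, taken as constant. Blinding and a common instruction make p the same in both arms, so the between-arm bias is p×d − p×d = 0. What remains is added variance, p(1−p)d²:
- p = 0.05, d = 5 mg/dL: 0.05 × 0.95 × 25 = 1.19, an SD component of 1.1 mg/dL.
- p = 0.5, d = 30 mg/dL: 0.5 × 0.5 × 900 = 225, an SD component of 15 mg/dL.

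**4. Open-label part.** With a fasted baseline and no control arm, shift in mean change = p×d:
- 0.05 × 5 = 0.25 mg/dL
- 0.05 × 10 = 0.5 mg/dL
- 0.5 × 10 = 5 mg/dL
- 0.5 × 30 = 15 mg/dL

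This applies to subjects who start at a Baseline visit. Among those who switch, 8.1 says "Subjects that received placebo will start the scheduled visits from a Baseline visit", whereas those already on active treatment continue their existing schedule. Groups A, B and C share the same instruction, so comparisons among them stay non-differential.

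**5. PK if one dose is taken fasted.** The model is one-compartment, twice-daily steady state, with all earlier doses fed and the last dose scaled by 1/f. With fast absorption, concentration relative to an all-fed course = 1 − (1 − 1/f)(1 − 2^(−12/h)), where h is the half-life in hours. For f = 2.6 and h = 12: 1 − 0.615 × 0.5 = 0.69. Ranges below cover sampling at 4 to 7.9 h and ka from 0.2 to 2/h.

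| Half-life (h) | f = 2.6 (3.2, high-fat meal) | f = 1.3 (assumed) |
|---|---|---|
| 6 | 0.54–0.68 | 0.83–0.88 |
| 12 | 0.69–0.81 | 0.88–0.93 |
| 24 | 0.82–0.89 | 0.93–0.96 |
| 48 | 0.90–0.94 | 0.96–0.98 |

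The 2.6-fold column is a worst case, because an ordinary breakfast need not be a high-fat, high-calorie meal.

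**6. What afternoon visits give the PK analysis.** A morning visit at 08:00–11:00 after an evening dose at 18:00–21:00 samples 11 to 17 h after dosing. An afternoon visit at 12:30–17:00 after a dose at 06:30–09:00 samples 3.5 to 10.5 h after dosing. Requiring mornings at every visit would therefore leave no sample earlier than about 11 h.

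**The case against.** **The plan can be followed as written.** Section 9.7 does not require afternoon visits. A morning visit, or one at least 8 hours after breakfast, satisfies every rule. This stands, and it is why the share affected may be near zero. It does not help a subject who is booked at 13:00.

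**The afternoon sentence may mean only that the dose is not to be held.** On that reading the tablet is taken at its usual time without food and the fast survives. The wording allows it, but 8.4.1 defines the usual dose as following breakfast, and the problem then moves to the PK sample.

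**The gap may be a product of missing text.** A reader might infer that the trial has no means of identifying non-fasted samples. The documents do not support that. Tables 3 and 4, the glycemic row of Table 6 and the exploratory analysis section cannot be read, and the manual of procedure, eCRF and separate SAP are not among the documents. Any of them could record meal time or contain a rule. What can be said is narrower: the items named in 9.7 are dose and sample times. A short interval marks a visit as at risk but does not show whether the subject ate. The readable laboratory analysis text (11.3.2) has no rule for non-fasted values.

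**Little depends on it.** The histology and clinical endpoints do not use fasting values, the Synopsis describes the open-label part as exploratory, and HbA1c does not depend on fasting. This stands and sets the severity.

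**Conclusion.** The conflict is real in the current text for visits less than 8 hours after breakfast, and it is minor. Followed literally, 9.7 yields non-fasted glucose, insulin, C-peptide, HOMA-IR and triglycerides at those visits. The alternative branch yields a PK sample that does not represent fed dosing.

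The effect is confined to:
- exploratory endpoints of the randomized part, as non-differential noise at week 72;
- open-label secondary kinetics endpoints, as a possible upward shift from a fasted baseline (0.25 to 15 mg/dL for glucose over the assumed range);
- the population PK analysis.

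A reader might infer a biased comparison of Aramchol with placebo, or a threat to the primary or key secondary endpoints. Neither follows: both arms receive the same blinded instruction, and those endpoints rest on biopsy and adjudicated events. Nor do the documents show that many visits are affected. The magnitudes are illustrations on assumed inputs, and material that cannot be read may already resolve the point.

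**What to change.** 1. **Amend 9.7 and the fasting statements together** (8.2.3 to 8.2.6, 8.2.8, 9.9.2). Schedule visits that supply fasting endpoints, at least weeks 12, 24, 48 and 72, in the morning with dose and breakfast held until after sampling, or at least 8 hours after breakfast. If other PK visits stay in the afternoon with a fed dose, state in the fasting sections that the fast is waived there and that those samples are not fasting values. Changing 9.7 alone to tell afternoon attendees to eat breakfast would direct what the other sections forbid.
2. **Record time of last meal and fed or fasted status of the last dose** at each laboratory or PK visit, if not already captured.
3. **Flag samples drawn less than 8 hours after a meal as non-fasted.** Analyse the fasting parameters with and without them, and make food state available as a population PK covariate.

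**Cost.** Wording changes in several sections, one or two eCRF fields, and a small additional analysis with fewer values. PK samples a few hours after a dose are given up at visits moved to the morning. If weeks 12, 24, 48 and 72 all move, 4 of the 8 visits to week 72 (weeks 4, 8, 36 and 60) can still supply them. If the sponsor already has a reconciling rule elsewhere, a cross-reference in 9.7 and agreement among the sections would be enough.
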